 - c) greater improvement or lesser impairment of quality of life after reconstruction of floor of lesser pelvis
2. To study if the different rehabilitation programmes used reflect differences in outcome measures in subgroup analyzes for both methods of reconstruction
3. To compare the health economic costs with the two techniques and to perform a cost-utility analysis (QALYs gained). The health economic analysis is optional to participating centres. Costs and health economics will be calculated only in centres that have routine registration (in electronic databases) of operation time, time at ICU, days in hospital, connected reoperations, connected readmissions and outpatient visits related to the index operation.

Investigational plan

Endpoints of study

1. Primary endpoint: Performance in Timed-stands test (TST)[9, 10]reflecting physical performance at 6 months from operation.
2. Secondary endpoints:
 1. Change in physical performance (3 months, 6 months and 1 year compared to preoperative)
 2. Primary wound healing assessed with the Southampton Wound Assessment Scale (SWAS)[11] at 3 months from operation
 3. Complications according to classification by Dindo-Clavien[12] (3 months, 6 months and 1 year)
 4. Proportion of persistent perineal sinus or fistula (3 months, 6 months, 1 year)
 5. Ability to sit (3 months, 6 months, 1 year)
 6. Change of pain and discomfort in gluteal region measured with VAS (3 months, 6 months and 1 year compared to preoperative)
 7. Change of quality of life measured with EQ-5D and EORTC forms C30 and CR29 (3 months, 6 months and 1 year compared to preoperative)
 8. Quality of life spot measures at 3 months, 6 months and 1 year

9. Length of hospital stay, costs of surgical treatments and QALYs gained at one year
10. Local recurrence during study period

Hypotheses of study

Primary hypothesis:

1. The reconstruction of lesser pelvis floor with APCI will result in better physical performance in operated patients compared to patients operated on with GMF.

Secondary hypotheses:

1. The assumed decrease of physical performance after the APCI operation will be less than after the GMF operation.
2. The reconstruction of lesser pelvis floor with APCI will result in better wound healing and less wound complications than the GMF operation.
3. The reconstruction of lesser pelvis floor with APCI will result in better ability to sit and lesser pain and discomfort in the gluteal region than the GMF operation,

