Once per year an independent advisor that together with the PI has the authority to stop the study if serious unexpected safety issues can be observed will evaluate the collected data of clinical adverse events. If the independent advisor and the PI make a decision to stop the study, the decision must be written and motivated in detail and distributed to all participating centres without delay.

Quality control and quality assurance

To ensure accurate and reliable data the study administration will do the following:

- Provide instructional material to the study sites, as appropriate (manual for physical examination etc.)
- Update study homepage at www.norrandskirurgi.se with relevant information and study material
- Start-up training, meeting with investigators
- Be available for consultation
- Conduct quality review of database (a monitor may be sent to participating centres)

Data analysis methods

Sample size

The sample size is calculated with the following assumptions:

- Estimated proportion of patients with low performance in TST with GMF 63%
- Estimated proportion of patients with low performance in TST with APCI 30%
- Estimated loss of data/cases 20% (mortality etc.)

The calculation gives that a total of 108 patients (54 patients in each study arm) are needed with 90% power and a significance level of 0.05 (alpha).

If the anticipated three-year inclusion phase of the study is too short for including 108 patients an alternative power calculation with 80% power will be used instead and the study will include a total of 80 patients only before the inclusion phase will be closed.

Interpretation of noninferiority

The noninferiority margin for the study is set on the basis of a minimally important clinical effect, which is a subjective judgement of the best expertise available. This approach remains the only alternative since there are no historical placebo controlled trials in the field for guidance and for practical reasons such trials are not possible to conduct.

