Preoperative oncologic treatment and pre- and postoperative tumour classification (cTNM and pTNM) will be registered in (and retrieved from) the Swedish Colorectal Cancer Registry for Swedish patients and for patients outside Sweden a similar form with TNM data is completed via the study homepage web application by the local investigator. The pTNM classification will also be included in the summary reports.

Primary analysis

Performance in Timed-stands test (TST) measured in seconds (time) will be compared between study arms at 6 months from the operation and tested with appropriate statistical tests. The proportion of patients that perform worse than the upper limit of reference values may be used as a parameter for comparison. TST reflects physical performance that is the primary outcome of the study.

Secondary analyses

1. The change of physical performance, i.e. the difference between preoperative and postoperative results in TST at 3, 6 and 12 months will be compared between study arms.
2. Primary wound healing at 3 months is categorized in subclasses (SWAS[11]) and the proportions of patients in different classes are compared between study arms.
3. Complications are categorized according to classification by Dindo-Clavien [12] and the proportions of patients in different classes are compared between study arms at 3, 6 and 12 months.

4. Ability to sit is defined in three classes and the proportions of patients in different classes are compared between study arms at 3, 6 and 12 months.
5. Pain and discomfort in gluteal region measured with VAS and analyzed with appropriate statistical methods. Comparisons will be done at 3, 6 and 12 months.
6. Quality of life is measured with EQ-5D and EORTC forms C30 and CR29 and the individual responses are calculated to a health utility index using an appropriate table/tariff for the general population[25, 26] Spot measures at 3, 6 and 12 months and differences between pre-treatment and postoperative measurements will be compared.
7. The proportion of patients that present local recurrence during the study period will be compared between study arms.

Subgroup analyses

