1. Costs of surgical treatments and QALYs gained are calculated for a subpopulation of the study population. Registration of parameters needed for the health economic calculations is optional for the participating centres and the subpopulation will be included only from centres that collect health economic data in their computer systems. Costs of surgical treatments including surgical complications up till 12 months will be calculated according to health economic standards and QALYs gained will be compared between study arms.
2. Two different rehabilitation programmes will be used for study patients and every participating centre must decide which of the programmes to use. The centre must stay to the chosen rehabilitation programme throughout the study. A subgroup analysis will be performed with the aim to reveal if the rehabilitation program has an impact on the main and secondary outcomes.

Safety analyses

An independent observer will be appointed with the task to contact each centre yearly and ask for unforeseen adverse events and problems. If severe adverse events occur the PI and the independent observer have the responsibility to decide whether the study can continue or should be stopped.

All safety analyses comparing the treatment groups will be performed based on the intent-to-treat population. All statistical tests of safety will be conducted at a two-sided alpha-level of 0.05. The safety analysis variables include, but are not restricted to:

- Postoperative mortality in 30 days
- Postoperative complications Grade IIIb or higher according to Dindo-Clavien
- Proportions of serious adverse events

Interim analyses

Interim analyses will be performed only if the study inclusion period exceeds 5 years. Safety analyses are exceptions that are performed whenever proposed by the independent observer.

Informed consent, ethical review and regulatory considerations

Informed consent

The informed consent document with study information will be used to explain in simple terms to patients what participation in the study means for the patient. The patient will get information of the risks, benefits and the alternatives available.

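### TST change and quality of life (compared both as spot values and as change) would be analysed more precisely, and tested once, with a single baseline-adjusted comparison per outcome

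*Protocol*

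**What the plan says.** Protocol, section Secondary analyses:

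- Item 1 (TST): "the difference between preoperative and postoperative results in TST at 3, 6 and 12 months will be compared between study arms".
- Item 6 (EQ-5D, EORTC C30 and CR29): spot values at 3, 6 and 12 months are compared, and in the same sentence "differences between pre-treatment and postoperative measurements will be compared". The section Endpoints of study lists these as two secondary endpoints, number 7 (change) and number 8 (spot).
- Item 5 (pain and discomfort) leaves the method open and does not mention change. Only the endpoint list defines it as change, in endpoint 6: "Change of pain and discomfort in gluteal region measured with VAS (3 months, 6 months and 1 year compared to preoperative".
- Items 2, 3, 4 and 7 compare proportions and involve no change score.

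No item names a baseline-adjusted model, and none rules one out. The section Interpretation of noninferiority allows secondary outcomes to inform which operation is preferred if noninferiority is found.

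**The concern.** In a randomised trial the preoperative means are equal in expectation. The arm difference in mean follow-up value and the arm difference in mean change therefore estimate the same quantity. Item 6 asks for both at each visit and gives no rule for the case where they disagree. The two statistics are only moderately correlated, so disagreement is not rare.

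Neither is the efficient choice. The spot value ignores the preoperative measurement. Simple change gives it a fixed weight of one, which is too much unless the correlation is near one. Below a correlation of 0.5, change is less precise than ignoring baseline altogether.

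Secondary hypothesis 1 (loss of physical performance) and secondary hypothesis 4 (quality of life) rest on items 1 and 6. Because secondary outcomes may inform the preferred operation, it matters that each gives one answer, as precisely as the data allow.

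**Working it through.** **1. Inputs from the protocol (section Sample size).** "Estimated proportion of patients with low performance in TST with GMF 63" per cent, "Estimated proportion of patients with low performance in TST with APCI 30" per cent, "90% power and a significance level of 0.05 (alpha"), 20% loss, 108 patients. If recruitment is slow, "an alternative power calculation with 80% power will be used instead", with 80 patients. A two-sided level is stated only for safety (section Safety analyses): "All statistical tests of safety will be conducted at a two-sided alpha-level of 0.05".

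**2. The plan's own figure.** Unpooled two-proportion formula, two-sided 0.05:

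n = (1.96 + 1.2816)² × (0.63×0.37 + 0.30×0.70) / 0.33² = 42.75 per arm; 42.75/0.8 = 53.4, so 54 per arm and 108 in total.

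With 80% power, n = 31.94; 31.94/0.8 = 39.9, so 40 per arm and 80 in total.

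Both stated sizes reproduce. Evaluable patients are 54 × 0.8 = 43 and 40 × 0.8 = 32 per arm. The protocol states no figure for the secondary analyses.

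**3. Assumptions.** Equal SDs at baseline and follow-up, set to 1; baseline/follow-up correlation rho = 0.3, 0.5 or 0.7; two-sided 0.05 for each test; preoperative values not influenced by allocation. The protocol gives no rho and no effect size for any secondary outcome.

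**4. Variances.** Spot: 1. Change: 2(1−rho). Adjusted for baseline: 1−rho². Adjusted relative to change: (1−rho²)/[2(1−rho)] = (1+rho)/2.

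**5. Power** = Φ(d/√(2v/n) − 1.96). With an illustrative effect of d = 0.5 SD:

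| rho | v, change | v, adjusted | ratio | change vs adjusted, 43 per arm | change vs adjusted, 32 per arm |
|---|---|---|---|---|---|
| 0.3 | 1.40 | 0.91 | 0.65 | 50% vs 68% | 39% vs 55% |
| 0.5 | 1.00 | 0.75 | 0.75 | 64% vs 76% | 52% vs 64% |
| 0.7 | 0.60 | 0.51 | 0.85 | 85% vs 90% | 73% vs 80% |

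Example, first row: 0.5/√(2.8/43) = 1.96, so power is Φ(0.00) = 50%; 0.5/√(1.82/43) = 2.43, so power is Φ(0.47) = 68%. The spot value has 64% (43 per arm) or 52% (32 per arm) at every rho.

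**6. TST at the planned effect.** If times are normal with equal SDs and one cut-off defines low performance, 63% against 30% implies d = 0.332 + 0.524 = 0.856 SD. At 43 per arm, change against adjusted is:

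- rho 0.3: 91.9% vs 98.6%, a gain of about 7 points
- rho 0.5: 97.8% vs 99.6%, a gain under 2 points
- rho 0.7: both above 99.9%

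At 32 per arm the gain is larger: 82.5% vs 94.9% at rho 0.3, and 92.9% vs 97.7% at rho 0.5.

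**7. Testing spot and change together.** Their covariance is 1−rho, so their correlation is (1−rho)/√(2(1−rho)) = √((1−rho)/2) = 0.59, 0.50 and 0.39 at rho 0.3, 0.5 and 0.7. With no true effect, the bivariate normal probability that at least one is significant at 0.05 is 8.8%, 9.1% and 9.4%. With a true 0.5 SD effect and 43 per arm, one is significant and the other is not in 31%, 31% and 33% of trials.

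**The case against.** The strongest reply is that the protocol names no test. To say that a difference is compared does not exclude a model of the change with the preoperative value as covariate. That model gives the same arm estimate as an adjusted analysis of the follow-up value, and covariate choice for secondary outcomes can be left to an SAP. This stands as far as it goes: unadjusted comparison is the plain reading of items 1 and 6, not something they state, and the precision figures apply only on that reading. It does not answer the duplication in item 6, where two comparisons of one effect are promised and neither is ranked.

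A reader might infer that all secondary outcomes are compared as unadjusted change. The protocol does not support that. Four of the seven items are proportions, and item 5 leaves the method open and so already permits the adjusted analysis.

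A reader might also infer bias, because change over-corrects a chance baseline imbalance. But the spot value under-corrects it, and over repeated randomisation neither is biased.

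It is also true that the size rests on an assumed rho, and for quality of life on an assumed effect. Change is not always the poor choice: it is more precise than the spot value once rho exceeds 0.5. Finally, the noninferiority section permits conclusions from secondary outcomes but ties no decision to any single test.

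**Conclusion.** The point holds for items 1 and 6, as a matter of precision and duplicate testing.

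- **Duplication (item 6).** One arm effect is tested twice per scale and visit with no lead analysis. The chance of at least one false positive is about 9% per pair, if each test is at two-sided 0.05. This changes little over rho 0.3 to 0.7.
- **Precision (items 1 and 6, unadjusted reading).** Adjustment cuts the variance to 0.65 to 0.85 of that of change over the same range. At a 0.5 SD effect and 43 per arm, that is worth 5 to 18 points of power. For TST at the planned effect and size it is worth about 7 points at rho 0.3 and under 2 at rho 0.5.

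TST at 6 months also appears both as spot value (primary) and as change (secondary), but there the primary label already says which leads. The primary analysis and the sample size of 108 are not called into question. This is a free improvement, not a defect that undermines the trial.

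**What to change.** In items 1 and 6, make one analysis per outcome inferential: the between-arm comparison of the 3, 6 and 12 month values, adjusted for the preoperative value of the same measure, by ANCOVA or a repeated-measures model. Report spot means and mean changes by arm descriptively. For TST at 6 months, the primary comparison stays the lead result.

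The change endpoints can keep their names, since modelling change or follow-up value with the same baseline covariate gives the same arm estimate. Quality-of-life endpoints 7 and 8 would then be served by one test.

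Item 5 needs only the same model named, so that it agrees with the change definition in endpoint 6.

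The cost is the wording of these items. The preoperative TST, VAS and quality-of-life measurements are already scheduled, so no data, visits or patients are added.

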4. The reconstruction of lesser pelvis floor with APCI will result in better quality of life than the GMF operation.
5. The reconstruction of lesser pelvis floor with APCI will result in lower costs of treatment and more QALYs gained than the GMF operation.
6. The local recurrence rate is not related to the method of reconstruction of lesser pelvis

Noninferiority hypothesis:

1. The reconstruction of lesser pelvis floor with APCI will result in clinically equivalent physical performance provided that results will be within defined noninferiority margins, see below.

Noninferiority margin:

The noninferiority margin is set to 10%. Interpretation, see section Data analysis methods.

Summary of study design

The study is multi-centre, prospective randomised and with parallel assignment. Centres that treat locally advanced rectal cancers with the extended abdominoperineal excision of rectum (EAPE)[7] can participate provided that:

1. the operative technique is standardized according to this protocol, see section Surgical methods
2. the centre/unit has resources for examinations of participants by a physiotherapist or a nurse
3. the centre/unit has one investigator in charge of the study locally
4. the centre/unit has an operative volume that enables at least 6 patients to be included/randomised during the anticipated three year study phase for inclusions

Centres that do not operate the rectal cancers included in this study can participate by arranging the preoperative examination and physical tests as well as follow-up of patients that are referred to other centres for the operation. In these cases the operating centre cares for the randomisation, operation and start of postoperative rehabilitation while the study follow-up and final rehabilitation can be completed at the patients' primary referral

hospital. The primary referral hospital needs a site investigator in charge of study patients just like centres that do the operations.

Patients with primary or recurrent cancers of rectal origin can be included but individual patients can be included only once. Concomitant therapies are allowed and preoperative or postoperative radiation therapy and/or chemotherapy may be given or not according to local multidisciplinary team (MDT) decisions.

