Blinding in surgical studies is hard to accomplish. This study is performed without attempts for blinding and thus the attending surgeon, the examiner of physical performance and the patient do not have to be blinded.

Concomitant therapy

Pre- and postoperative radiotherapy or chemo radiotherapy can be utilised according to multidisciplinary team decisions at each centre.

Postoperative rehabilitation programmes

Due to already existing routines, we consider it not realistic to prescribe only one uniform programme. Instead, the patients will be allocated to either an established programme[7] or to an accelerated programme that has been used in another centre. Both rehabilitation programmes are standardized, written and should be followed explicitly. The descriptions of both programmes can be downloaded from the study webpage at www.norrlandskirurgi.se.

Participating centres must choose one of the rehabilitation programmes and use that program for all their study patients. The rehabilitation programmes at hand are studied earlier and considered safe [21].

Evaluation of outcome measures and safety

Measures of physical performance

The study physiotherapist or nurse will examine measures of physical performance.

A "timed-stands test" is to be performed by recording the time needed to stand ten times from a standard chair[9, 10]. The test gives a measure of lower extremity muscle strength, muscle coordination and tenderness of the gluteal region (caution when sitting) and gives the possibility to correlate the results to a reference population studied earlier[9]. The test is validated.

A complementary step test is performed at some participating centres (optional test)[22].

The study physiotherapist or nurse will process measures of quality of life, pain, discomfort and ability to sit. Data will be registered on forms (see Appendix) or directly in the electronic database.

Quality of life is measured with the global instrument EQ-5D and the cancer specific instrument EORTC QLQ-C30 and QLQ-CR29. The forms will be sent to the patient prior to the follow-up visits and the study physiotherapist or nurse who cares for the data to be registered in the study database will collect the completed forms. Completeness of data should be checked during the visit so that any incomplete data can be corrected together with the patient.

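### The one-year QALY comparison is confined to centres with electronic cost data, a condition it does not need, which costs precision and representativeness in a secondary analysis

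*Protocol*

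**What the plan says.** **The restriction.** Item 1 of the Subgroup analyses section of the protocol says "Costs of surgical treatments and QALYs gained are calculated for a subpopulation of the study population". It adds that "Registration of parameters needed for the health economic calculations is optional for the participating centres" and that "the subpopulation will be included only from centres that collect health economic data in their computer systems". It also plans a comparison of QALYs between the arms. Secondary objective 3 sets the same condition: "Costs and health economics will be calculated only in centres that have routine registration (in electronic databases) of operation time", followed by intensive-care time, hospital days, reoperations, readmissions and outpatient visits.

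**Where QALYs appear as an outcome.** Secondary endpoint 9 reads "Length of hospital stay, costs of surgical treatments and QALYs gained at one year". Secondary hypothesis 5 predicts that the collagen implant "will result in lower costs of treatment and more QALYs gained than the GMF operation". Neither entry names a population.

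**What is collected everywhere.** Under Measures of physical performance, "Quality of life is measured with the global instrument EQ-5D and the cancer specific instrument EORTC QLQ-C30 and QLQ-CR29". The study design summary and the flowchart place quality-of-life registration before treatment and at 3, 6 and 12 months. Secondary analysis 6 converts responses to a utility index and compares visit values and changes between arms, with no limit by centre. The Discontinuations section has site investigators record deaths and losses to follow-up through the web application.

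**The concern.** The restriction fits one of the two quantities it covers. Every item in the list in objective 3 is an input to cost, and none is an input to a QALY. By tying the two together, the plan makes the QALY comparison depend on hospital data systems, although the utilities and deaths it needs come from all centres.

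At stake is the QALY part of secondary endpoint 9 and hypothesis 5. Under Interpretation of noninferiority, the protocol allows secondary outcomes to guide which operation is preferred if the main outcome shows noninferiority, so the QALY result could carry some weight. Each centre also uses a single rehabilitation programme for all its patients. A subset of centres may therefore have a different mix of programmes from the whole trial.

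**Working it through.** **1. Does a QALY need the restricted data?**

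| Needed for | Item | Where collected |
|---|---|---|
| QALY | EQ-5D before treatment, 3, 6, 12 months | Every centre; not marked optional, whereas the step test and the sensory tests are |
| QALY | Conversion to a utility index | Planned in secondary analysis 6 with no centre limit |
| QALY | Deaths | Every centre, through the web application |
| Cost | Operation time, intensive care, hospital days, reoperations, readmissions, outpatient visits | Only centres with routine electronic registration |

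Only the cost rows depend on the restriction.

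**2. The plan's own sample size.** The protocol gives no figure for QALYs, so the only figure to reproduce is the total. Inputs from the Sample size section are 63% and 30% with low performance, alpha 0.05 (two-sided assumed) and 20% loss. With the unpooled two-proportion formula:

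- 90% power: n per arm = (1.960 + 1.282)² × (0.63×0.37 + 0.30×0.70) / 0.33² = 42.75, so 43. Then 43/0.8 = 53.75, so 54 per arm and 108 in total.
- 80% power: n per arm = 31.94, so 32. Then 32/0.8 = 40 per arm and 80 in total.

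Both match the protocol and are not affected by this point. Removing the 20% loss leaves about 86 patients (108 × 0.8 = 86.4), or 64 under the fallback (80 × 0.8).

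**3. Loss of precision.** Let f be the share of patients in cost-registering centres. With equal arms, the standard error of the QALY difference is SD × √(4/N). Replacing N by fN multiplies it by 1/√f. The difference detectable with 80% power at two-sided 0.05 is (1.960 + 0.842) × √(4/(fN)), in SD units. The values of f are assumptions, since the protocol gives none.

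| f | Standard error ratio | Detectable, N = 86 | Detectable, N = 64 |
|---|---|---|---|
| 1 | 1.00 | 0.60 SD | 0.70 SD |
| 0.75 | 1.15 | 0.70 SD | 0.81 SD |
| 0.50 | 1.41 | 0.85 SD | 0.99 SD |
| 1/3 | 1.73 | 1.05 SD | 1.21 SD |

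Worked case, f = 0.50 and N = 86: 2.802 × √(4/43) = 0.85.

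The QALY denominator need not be 86 or 64. The protocol's 20% loss includes mortality, and patients who die still contribute to a QALY. The ratio column does not depend on N.

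**The case against.** **The subset has a purpose.** Objective 3 introduces QALYs as the effect side of a cost-utility analysis, and cost per QALY needs both quantities in the same patients. This stands for costs and for the ratio. It does not cover the separate between-arm comparison of QALYs that the same item plans.

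**The EQ-5D data are still used.** A reader might infer that EQ-5D from the other centres is thrown away. The protocol does not support that, because secondary analysis 6 compares utilities at each visit in all patients. What is missing is their combination over the year with survival, which separate visit comparisons do not provide.

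**The comparison stays randomised.** A reader might infer that a subset of centres that opted in biases the comparison between arms. The protocol does not support that either. Whole centres enter or stay out according to their data systems, and randomisation is stratified by centre, so each included centre keeps its own randomised comparison.

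**The protocol does not clearly contradict itself.** A reader might take endpoint 9 and hypothesis 5 as promising QALYs for the whole trial. They name no population, they list costs in the same unrestricted way, and objective 3 discloses the limit close to the endpoint list.

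**The size is unknown.** This stands. If nearly all patients are in cost-registering centres, f is near 1 and the loss is negligible.

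**Conclusion.** The point holds as a minor one about a secondary analysis. As written, the protocol limits the one-year QALY comparison by a cost-data condition that QALYs do not depend on. The harm is a standard error larger by 1/√f, and a result that describes only the centres with suitable systems. The factor is 1.15, 1.41 or 1.73 if 75%, half or one third of patients are in such centres. With 86 evaluable patients, a subset of half raises the detectable difference from 0.60 to 0.85 SD.

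These sizes rest on assumed values of f, and the detectable differences also rest on an assumed evaluable number. The primary endpoint, the sample size, the safety analyses and the all-patient quality-of-life comparison are not affected. The restriction is stated outright in two places, so an analysis plan that follows the protocol would carry it over.

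**What to change.** Reword item 1 of the Subgroup analyses section, and secondary objective 3 to match:

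- Calculate QALYs to 12 months, and compare them between arms, in the full intention-to-treat population as the protocol defines it. Use the EQ-5D collected at every centre and count deaths.
- Restrict only costs and the cost-utility ratio to centres with resource-use data.
- Report the QALY difference in that subset beside the full-population one, so that readers can judge whether the cost-utility result rests on a typical part of the trial.

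The cost is a small change of wording in two places and slightly more analysis work. No new data, visits or patients are needed.
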